#### Mechanical Lens Fit (Test Lens)

The estimated sample size to test the primary hypothesis (H0 PT  $\leq$  P0, H1: PT > P0) is 100. The sample size was calculated using PROC POWER for one sample proportion using an exact Test of a Binomial Proportion.

#### Visual Performance (logMAR)

Sample size calculation for visual performance (logMAR) was carried out using an approximation of the power of an F-test derived from the non-centrality parameter calculated form the observed F statistic of a linear model.

Model details:

visual performance was analyzed using a linear mixed model. Lens type was included as the only fixed effect. A compound symmetric (CS) covariance matrix was used to model the correlation between measurements within the same subject. Below is the variance-covariance matrix used in the visual performance model.

$$\sum_{Visual \ Acuity} \begin{pmatrix} 0.004047 & 0.002894 \\ 0.002894 & 0.004737 \end{pmatrix}$$

#### Slit Lamp Findings

There were no Grade 3 or higher SLFs observed in any of the historical studies. Assuming no difference between study lenses and a correlation 0.70 between left and right eyes within the same subject (intra-subject correlation), a reference rate of no more than 5% was assumed (worse-case scenario) with a non-inferiority odds ratio margin of 2. A total of 2000 replicating trials were simulated, each replicated sample was analyzed using a generalized estimating equation (GEE) model with a binary distribution and the logit as the link function. Each model included lens type as the only fixed, eye was included as a random effect. The Odds ratio and corresponding 95% confidence interval was used estimate differences between the Test and Control lenses. The upper limit of each 95% confidence interval was compared to 2; if the upper limit was below 2 then NI=1; otherwise NI=0. Statistical power was calculated at the average NI. A sample size of 224 (112 per arm) was chosen to achieve a minimum statistical power of 80%.

Using a reference rate for the control that does not exceed 5% and no more than a 5% difference between the Test and Control lenses translates to an odds ratio margin of 2. A reference rate of 5% was used since this is the worst-case scenario.

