$$\sum_{Visual\ Acuity} \begin{pmatrix} 0.004047 & 0.002894 \\ 0.002894 & 0.004737 \end{pmatrix}$$

Slit Lamp Findings

There were no Grade 3 or higher SLFs observed in any of the historical studies. Assuming no difference between study lenses and a correlation 0.70 between left and right eyes within the same subject (intra-subject correlation), a reference rate of no more than 5% was assumed (worse-case scenario) with a non-inferiority odds ratio margin of 2. A total of 2000 replicating trials were simulated, each replicated sample was analyzed using a generalized estimating equation (GEE)

model with a binary distribution and the logit as the link function. Each model included lens type as the only fixed, eye was included as a random effect. The Odds ratio and corresponding 95% confidence interval was used estimate differences between the Test and Control lenses. The upper limit of each 95% confidence interval was compared to 2; if the upper limit was below 2 then NI=1; otherwise NI=0. Statistical power was calculated as the average NI. A sample size of 224 (112 per arm) was chosen to achieve a minimum statistical power of 80%.

Using a reference rate for the control of 5% and no more than a 5% difference between the Test and Control lenses translate to an odds ratio margin of 2. A reference rate of 5% was used as the worst-case scenario.

Individual Questionnaire Items

Vision satisfaction in bright lighting sample size estimates were calculated using historical data from CR-5960.⁷ One-thousand boot strap samples were simulated based on the historical data. For each replicated sample a generalized linear mixed model was used with a multinomial distribution and the cumulative logit as the link function. Lens type was included in the model as the only fixed effect.

Using a reference rate of 50% for the Control lens and assuming no difference between the Test and Control a 10% difference translate to a cumulative odds ratio margin of 0.67. the reference rate of 0.50 was used as the worst-case scenario.

Endpoint	Number per Subjects to Complete	Power
Distance Monocular Visual Acuity (logMAR)	30	86%
SLFs (Grade 3 or Higher)	224	80%
Acceptable lens Fit (Test Lens Only)	100	82%
CLUE Comfort	224	87%
Vision Satisfaction in Bright Lighting	40	87%

Table 12: Sample Size Estimates and Power Calculations for Primary Endpoints

Endpoint	Number per Subjects to Complete	Power
CLUE Handling	224	63%
CLUE Overall Quality of Vision	224	71%

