#### Vision Satisfaction

Vision satisfaction in bright lighting sample size estimate was calculated using historical data One-thousand boot strap samples were simulated based on the historical data. For each replicated sample a generalized linear mixed model was used with a multinomial distribution and the cumulative logit as the link function. Lens wear was included in the model as the only fixed effects.

Using a reference rate of 0.50 for the Control lens and assuming no difference between the Test and Control a 10% difference translate to a cumulative odds ratio margin of 0.67. the reference rate of 0.50 was used since this is considered to be the worst-case scenario.

	Number per Subjects to	
Endpoint	Complete	Power
Distance Monocular Visual Acuity (logMAR)	30	86%
SLFs (Grade 3 or Higher)	224	80%
Acceptable lens Fit	100	82%
CLUE Comfort	224	87%
Vision Satisfaction in Bright Lighting	40	87%

Table 11: Sample Size Estimates and Power	Calculations for Primary Endpoints
---	------------------------------------

Table12: Sample Size Estimates and Power Calculations for Secondary Endpoints

Endpoint	Number per Subjects to Complete	Power
CLUE Handling	224	63%
CLUE Overall Quality of Vision	224	71%

As indicated in Table 10 and 11 above, the sample size chosen for this study was primary driven by Slit Lamp Findings (Grade 3 or higher) and CLUE Comfort. The plan is to enroll 236 eligible subjects (118 subject per arm) with a target of 112 subjects to complete each arm in the study. During the enrollment period, the subject drop-out rate with be closely monitored, if an unexpectedly high dropout rate is observed, then the targeted total enrollment number maybe be increased accordingly to ensure that a minimum of 224 subjects complete the study.

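### The stated 80% power for Grade 3 or higher slit lamp findings does not follow from its stated inputs (about 23% with subject clustering), and the rule simulated is not the rule planned

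*SAP*

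**What the plan says.** **The power statement.** SAP 7.4 (Slit Lamp Findings) and the matching paragraph of Protocol 14.2 describe 2,000 simulated trials with no true difference, a 5% reference rate and a correlation of 0.70 between a subject's eyes. Each trial was analysed by a logit GEE with lens as the only fixed effect, and "eye was included as a random effect". For the decision, "The upper limit of each 95% confidence interval was compared to 2". The conclusion is: "A sample size of 224 (112 per arm) was chosen to achieve a minimum statistical power of 80" percent. SAP Table 11 (row "SLFs (Grade 3 or Higher") and Protocol Table 12 repeat 224 and 80%.

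**The link to the margin.** The SAP says that "no more than a 5% difference between the Test and Control lenses translates to an odds ratio margin of 2", and adds: "A reference rate of 5% was used since this is the worst-case scenario". The protocol agrees: "A reference rate of 5% was used as the worst-case scenario".

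**History.** "There were no Grade 3 or higher SLFs observed in any of the historical studies". SAP Table 9 counts 430 Test and 135 Control subjects.

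**The planned test.** SAP 10.1 and Protocol 14.5 plan a Bayesian logistic random-effects model. Non-inferiority needs the upper 95% credible limit of pT - pC to be below 0.05, and the SAP defines pT and pC as proportions of eyes. If Grade 3 or higher findings are too few, Grade 2 or higher findings are tested instead. The SAS code in SAP 14.1 computes P_C and P_T from the fixed effects alone.

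**Its weight.** This is one of five primary hypotheses that must all be met (SAP 4.1). Both documents name it as one of the two endpoints that drove the sample size.

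**The concern.** A 5% event rate leaves few events. With 224 eyes per arm there are about 11 affected eyes per arm, and the correlation of 0.70 makes them worth fewer still. Excluding an odds ratio of 2 with 80% probability on so little information looks implausible.

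The simulated rule also differs from the planned one in model, interval and scale, so even a correct figure would not be the power of the planned test. At stake is the stated basis for N = 224 on a primary safety endpoint. A reader of Table 11 is told of a power that the inputs do not give and that belongs to a different rule.

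**Working it through.** **Inputs** (SAP 7.4): n = 112 completers per arm, two eyes each; p = 0.05 in both arms; eye correlation 0.70; odds-ratio margin 2; two-sided 95% interval. Dropout does not enter, because power is stated for completers.

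**Attempt to reproduce the 80%, clustering by subject**

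- Effective eyes per arm = 2 × 112 / (1 + 0.70) = 224 / 1.7 = 131.8.
- SE(log OR) = sqrt(2 / (131.8 × 0.05 × 0.95)) = sqrt(2 / (131.8 × 0.0475)) = 0.565.
- Power = Φ(ln 2 / 0.565 − 1.96) = Φ(0.693 / 0.565 − 1.96) = **0.23**.

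Simulation agrees. An independence GEE with sandwich variance gives 0.23 over 100,000 trials (0.28 if 0.70 is a latent correlation). A fitted exchangeable GEE gives 0.21 over 2,000 trials. The stated 80% is not reproduced.

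**Other readings of the text, still at p = 0.05** (ranges cover binary and latent correlation)

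| Change | Power |
|---|---|
| Margin 2.11, from (0.10/0.90)/(0.05/0.95) | 26-32% |
| 90% interval | 34-39% |
| Clustering ignored | 38-39% |
| Clustering ignored and 90% interval | 49% |
| Eye as the GEE cluster, 95% or 90% interval | 69-76% |

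The last row is not a valid analysis: a sandwich variance cannot be estimated from two clusters.

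**The two rules respond to the event rate in opposite ways.** Both columns use 112 per arm and equal true rates. The odds-ratio column uses subject clustering and a binary correlation of 0.70. The risk-difference column is for population (marginal) rates of eyes only. Its range covers three methods and both readings of the correlation:

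- a cluster-robust Wald limit, whose actual error at the margin is 3.2-5.4%;
- the same limit recalibrated to 2.5% error;
- a simplified Bayesian logistic-normal model with a subject effect but no site effect or covariates.

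| True rate | Odds ratio below 2 | Risk difference below 0.05 |
|---|---|---|
| 5% | 23% | 44-57% |
| 4% | 19% | 51-66% |
| 3% | 14% | 61-77% |
| 2% | 9% | 74-89% |
| 1% | 3% | 89-98% |

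So, among rates up to 5%, 5% is the worst case on the difference scale and the best case for the odds-ratio rule that was simulated.

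**Plausible rates.** With no events in the historical subjects, the one-sided 95% upper bounds are 1 − 0.05^(1/430) = 0.7% (Test) and 1 − 0.05^(1/135) = 2.2% (Control).

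**What the SAP code compares.** It evaluates P_C and P_T with subject and site effects at zero. In a logistic-normal model, a population rate of 5% with a binary eye correlation of 0.70 implies a subject SD of about 7 and an intercept of about −11.9. The probability at a zero subject effect is then about 0.000007, not 0.05. In a simplified check (subject effect only, the coded subject-SD prior, 500 trials) with 5% in both arms, the coded difference met the rule in 100% (binary) and 99.8% (latent) of trials. The same fits on population rates met it in 47% and 50%. At a true 10% versus 5%, the coded difference still passed in 100% and 79% of trials. Its high pass rate is therefore a defect and not good power.

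**The case against.** The strongest reply has four parts.

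- **The wording allows another model.** The text speaks of eye as a random effect, and the program is not available. If eye is the GEE cluster, power is 69-76%. Adding the 2.11 margin and a 90% interval brings it to 77-80%. This stands as a reason not to claim to know how the 80% arose. It does not support the figure: the analysis is invalid, and the last step departs from the stated margin of 2 and 95% interval.
- **Power at realistic rates may be good.** Given the historical zeros this is fair. For population rates of 1-2%, approximate power on the difference scale is 74-98%. But the documents state 80% at 5%, under another rule.
- **The risk-difference ranges do not describe the coded analysis.** Correct. They hold only for population rates. The SAP's definition of pT and pC as proportions of eyes supports that estimand, but its code does not.
- **At very low rates Grade 3 may not be the endpoint tested.** Also correct. The fallback would apply the test to Grade 2 or higher, where the historical counts are 116 of 860 Test eyes and 83 of 270 Control eyes, both far above 5%. No power figure for Grade 3 covers that test.

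**Conclusion.** The power statement is wrong as written in both documents. Under the stated inputs with clustering by subject it is about 23% (28% with a latent correlation), and no reading tried that keeps the stated margin and interval reaches 80%. Separately, the odds-ratio rule is not the planned rule, and calling 5% the worst case is right only on the difference scale.

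A reader might go further in three ways that the documents do not support.

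- That the planned test has 23% power, or that 224 completers cannot give it 80% power at a 5% rate. The 23% belongs to the odds-ratio rule. The 44-57% at 5% assumes population rates, while the code as written would pass almost always.
- That the trial needs more patients. About 585 completers per arm would be needed for 80% under the odds-ratio rule, but that rule is not the planned test.
- That a 50% reference rate was entered by mistake. It does return 80% with the other inputs kept, but nothing in the documents shows that it was used.

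The consequence is limited to the justification of N. The margin, the decision rule and the sample size do not change.

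**What to change.** In SAP 7.4 with Table 11, and Protocol 14.2 with Table 12:

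1. Remove the 80% figure and the odds-ratio-2 simulation.
2. State that the rates compared are the population proportions of eyes, as SAP 10.1 words it, and align the code in SAP 14.1 with that.
3. Simulate the planned model and risk-difference rule at 112 per arm over equal true rates of 1% to 5%. Define the 0.70 correlation as binary or latent, check the pass rate when the true difference equals the 5-point margin, and report the resulting powers in the two tables.
4. State that these powers apply to the Grade 3 or higher test and not to the Grade 2 or higher fallback.
5. Where the text after the tables says that slit lamp findings drove the sample size, withdraw that statement or qualify it with the simulated result. Do not write a fixed conclusion about 80% power before the simulation is done, unless it is limited to population rates.

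The cost is one simulation, the code alignment, short text changes and one row in each table. The stated figure at 5% may be less favourable. No patients are added.

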#### Vision Satisfaction

Vision satisfaction in bright lighting sample size estimate was calculated using historical data One-thousand boot strap samples were simulated based on the historical data. For each replicated sample a generalized linear mixed model was used with a multinomial distribution and the cumulative logit as the link function. Lens wear was included in the model as the only fixed effects.

Using a reference rate of 0.50 for the Control lens and assuming no difference between the Test and Control a 10% difference translate to a cumulative odds ratio margin of 0.67. the reference rate of 0.50 was used since this is considered to be the worst-case scenario.

	Number per Subjects to	
Endpoint	Complete	Power
Distance Monocular Visual Acuity (logMAR)	30	86%
SLFs (Grade 3 or Higher)	224	80%
Acceptable lens Fit	100	82%
CLUE Comfort	224	87%
Vision Satisfaction in Bright Lighting	40	87%

Table 11: Sample Size Estimates and Power	Calculations for Primary Endpoints
---	------------------------------------

Table12: Sample Size Estimates and Power Calculations for Secondary Endpoints

Endpoint	Number per Subjects to Complete	Power
CLUE Handling	224	63%
CLUE Overall Quality of Vision	224	71%

As indicated in Table 10 and 11 above, the sample size chosen for this study was primary driven by Slit Lamp Findings (Grade 3 or higher) and CLUE Comfort. The plan is to enroll 236 eligible subjects (118 subject per arm) with a target of 112 subjects to complete each arm in the study. During the enrollment period, the subject drop-out rate with be closely monitored, if an unexpectedly high dropout rate is observed, then the targeted total enrollment number maybe be increased accordingly to ensure that a minimum of 224 subjects complete the study.

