2-Week Follow-up	0 (0.0)	0 (0.0)

¹The percent of any unacceptable fit is calculated using Total Unique eyes as a denominator

Table 10: Descriptive Summary of Slit Lamp Findings Pooled Across all Historical Studies

SLF Grade 2	Test n (%)	Control n (%)
Corneal Edema	0 (0.0)	0 (0.0)
Conjunctival Injection	59 (6.86)	59 (21.85)
Tarsal Abnormalities	51 (5.93)	24 (8.89)
Corneal Neovascularization	3 (0.35)	0 (0.0)
Corneal Staining	3 (0.35)	0 (0.0)
Other Findings	0 (0.0)	0 (0.0)
Total Eyes (N)	860	270
Any SLF Grade 2 ²	116 (13.48)	83 (33.74)
Any SLF Grade 3+	0 (0.0)	0 (0.0)
Total Unique Eyes	860	270
Total Unique Subjects	430	135

%= nx100/N; SD=Standard Deviation

¹All SLF reported for this study are combined for the purposes of summarizing
² The percent (%) of Any Grade 2 is calculated using the Total Unique Eyes as the denominator

Table 11: Descriptive Summary of Individual Item from - 2-Week Follow-up				
Questionnaire Item/ Response	Test	Control		
Vision Satisfaction in Bright Light [n(%)]				
Strongly Agree	72 (29.75)	51 (21.07)		
Agree	129 (53.31)	130 (53.72)		
Neither Agree Nor Disagree	24 (9.92)	21 (8.68)		
Disagree	17 (7.02)	33 (13.64)		
Strongly Disagree	0 (0.0)	7 (2.89)		

CLUE Comfort Scores

With respect to CLUE comfort, based on historical data from Period 1, a mean difference of 2 points was assumed and a standard deviation of 21, an additive equivalence test in PROC Power for two sample means was used to Test for non-inferiority. A non-inferiority margin of -5 points was used since this is considered to be no more than a 10% shift in the distribution of CLUE scores.

Mechanical Lens Fit (Test Lens)

The estimated sample size to test the primary hypothesis (H0 PT \leq P0, H1: PT > P0) is 100. The sample size was calculated using PROC POWER for one sample proportion using an exact Test of a Binomial Proportion.

Visual Performance (logMAR)

Sample size calculation for visual performance (logMAR) was carried out using an approximation of the power of an F-test derived from the non-centrality parameter calculated form the observed F statistic of a linear model.⁸

Model details:

visual performance was analyzed using a linear mixed model. Lens type was included as the only fixed effect. A compound symmetric (CS) covariance matrix was used to model the correlation between measurements on the same subject across study periods. Below is the variance-covariance matrix used in the visual performance model.

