# 7.4. Sample Size Justification

This study was designed and powered to show non-inferiority of the Test lens compared to the Control lens with respect to logMAR Visual Acuity, Slit Lamp Findings (Grade 3 or higher) and CLUE comfort. It was assumed there was no difference between the Test and Control lens with respect to slit lamp findings and a 1 letter difference (0.02) between the Test and Control lenses with respect to visual acuity logMAR. Based on data from 3 historical studies, it was assumed there was a 2-point difference between the Test and Control lenses with respect to CLUE comfort based on the summary statistics from the first period of the historical studies.

In addition to the endpoints mentioned above this study was also powered to demonstrate noninferiority of the Test lens relative to the Control lens with respect to vision satisfaction in bright lighting and the proportion of eyes with acceptable fitting while the Test lens is significantly superior to 90%.

Unless otherwise specified, the sample size was calculated to achieve a minimum statistical power of 80% and a type I error of 5%.

A total of 5 historical studies were utilized in the sample size calculation. Table 5 displays the studies, their corresponding study design and the number of subjects enrolled and completed perprotocol.

			No.	No. Completed
Study	Study Design	Endpoints Collected	Enrolled	Per-Protocol
	2X3 Crossover	CLUE, SLF Lens Fit	135	132
	2X3 Crossover	CLUE, Visual Acuity (logMAR), SLF, Lens Fit	133	121
	2X3 Crossover	CLUE, SLF Lens Fit	92	78
	Single-Arm	SLF, Lens Fit	54	48
	Single-Arm	SLF, Lens Fit	56	41

Table 5: Historical Studies Included in Sample Size Calculation

CLUE Domain [Mean(SD)  ]	Test	Control

Comfort	66.66 (21.066)	63.90 (24.197)
Handling	69.32 (18.454)	71.11 (20.429)
Overall Quality of Vision	64.49 (17.221)	64.44 (23.351)

SD = Standard Deviation

Table 7: Descriptive Summary of Visual Acuity (logMAR) - 2-Week Follow-up Evaluation-Period 1 Only

Visual Acuity High Illumination High Contrast	Test	Control
[Mean(SD)  ]	-0.088 (0.0862)	-0.0622 (0.0740)

SD = Standard Deviation

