#### Table 9: Descriptive Summary of Slit Lamp Findings Pooled Across all Historical Studies

SLF Grade 2	Test n (%)	Control n (%)
Corneal Edema	0 (0.0)	0 (0.0)
Conjunctival Injection	59 (6.86)	59 (21.85)
Tarsal Abnormalities	51 (5.93)	24 (8.89)
Corneal Neovascularization	3 (0.35)	0 (0.0)
Corneal Staining	3 (0.35)	0 (0.0)
Other Findings	0 (0.0)	0 (0.0)
Total Eyes (N)	860	270
	·	
Any SLF Grade 2 	116 (13.48)	83 (33.74)
Any SLF Grade 3+	0 (0.0)	0 (0.0)
Total Unique Eyes	860	270
Total Unique Subjects	430	135

%= nx100/N; SD=Standard Deviation

All SLF reported for this study are combined for the purposes of summarizing

 The percent (%) of Any Grade 2 is calculated using the Total Unique Eyes as the denominator

Table 10: Descriptive Summary of Individual Ite	em from – 2-Weel	- 2-Week Follow-up	
Questionnaire Item/ Response	Test	Control	
Vision Satisfaction in Bright Light [n(%)]			
Strongly Agree	72 (29.75)	51 (21.07)	
Agree	129 (53.31)	130 (53.72)	
Neither Agree Nor Disagree	24 (9.92)	21 (8.68)	
Disagree	17 (7.02)	33 (13.64)	
Strongly Disagree	0 (0.0)	7 (2.89)	

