## 7.5. Statistical Significance Level

All planned analysis will be conducted with an overall type I error rate of 5%. There will be neither adjustment for multiple tests nor adjustment for multiplicity of endpoints. Unless otherwise specified, all statistical tests will be 2-sided.

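### Bright-light vision satisfaction: the stated 87% power with 40 subjects is not the power of this two-arm parallel trial on its own 2-sided 95% rule, whether 40 is a total or per arm

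*SAP*

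**What the plan says.** The sizing text (SAP 7.4, Vision Satisfaction; protocol 14.2, Individual Questionnaire Items) describes a simulation: "One-thousand boot strap samples were simulated based on the historical data". Each sample was analysed with a cumulative-logit model in which lens was the only fixed effect. The protocol names the source: "Vision satisfaction in bright lighting sample size estimates were calculated using historical data from CR-5960". A separate paragraph derives the sizing margin: "Using a reference rate of 50% for the Control lens and assuming no difference between the Test and Control", a 10-point loss becomes a cumulative odds ratio of 0.67. The result is one table row: 40 subjects, 87% power.

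The text for this row does not say whether 40 is a total or per arm, which effect was simulated, what interval or success criterion was applied, or whether subjects or single ratings were resampled. The general sizing statement in SAP 7.4 is that "the sample size was calculated to achieve a minimum statistical power of 80% and a type I error of 5" per cent, with no sidedness.

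The trial itself is specified clearly. SAP 2.1 describes two parallel arms, and SAP 7.4 plans 112 completers in each. SAP 7.5 says "Unless otherwise specified, all statistical tests will be 2-sided". SAP 10.1 declares non-inferiority when the lower limit of the 2-sided 95% credible interval for the difference in positive-response proportions exceeds -0.10. SAP 4.1 requires every primary hypothesis to be met.

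**The concern.** Because all five primaries must pass, each row of the power table will be read as the chance that this trial passes that test. A reader of 40 subjects and 87% would conclude that 224 subjects leave a very large surplus for this endpoint and that the margin is easily cleared whatever the true effect. Both conclusions depend on the row describing this design and this rule. Three features suggest that it may not: 40 is small for a 10-point margin on a proportion, the historical CLUE studies are listed as "2X3 Crossover", and the sizing margin is an odds ratio while the decision rule is a difference in proportions.

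**Working it through.** **Inputs.** Historical responses (SAP Table 10, protocol Table 11): Test 72 + 129 = 201 of 242 positive, 83.06%; Control 51 + 130 = 181 of 242, 74.79%. Difference +8.26 points. A cumulative-logit fit to the two columns gives a log odds ratio of 0.5205 (odds ratio 1.68) with standard error 0.1751 at 242 per lens. Margins: -0.10 on the difference (SAP 10.1) and 0.67 on the odds ratio (SAP 7.4). Critical value 1.96.

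**Margin conversion.** At 50%: (0.40/0.60)/(0.50/0.50) = 0.667, as stated. At the historical Control rate of 74.8%: (0.648/0.352)/(0.748/0.252) = 0.62. So 0.67 equals ten points only at a 50% rate.

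**Attempt to reproduce 87% with 40 subjects.** Three measures were used, all with the historical effect, two independent arms and 2-sided 95%.

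1. Odds ratio against 0.67. Power = Φ[(0.5205 − ln 0.67)/SE − 1.96], with SE = 0.1751 × √(242/n).
 - n = 20 per arm: SE 0.609, power Φ(−0.448) = 33%.
 - n = 40 per arm: SE 0.431, power Φ(0.178) = 57%. Simulation gives 58%.
 - n = 112 per arm: SE 0.257, power Φ(1.618) = 95%.
2. Raw risk difference against -0.10. SE = √[(0.8306 × 0.1694 + 0.7479 × 0.2521)/n]; power = Φ[(0.0826 + 0.10)/SE − 1.96].
 - n = 20: SE 0.128, power 30% (simulation about 32%).
 - n = 40: SE 0.0907, power 52% (simulation about 53%).
 - n = 112: SE 0.0542, power 92%.
3. Model-based difference against -0.10. This takes the proportion in the top two categories from the fitted cumulative-logit model, which is the type of quantity the SAP 14.1 code forms. Power by simulation, maximum likelihood with lens as the only effect: 46-50% at 20 per arm, 75-78% at 40 per arm, 99% at 112 per arm.

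| Per arm | Odds ratio vs 0.67 | Raw difference | Model-based difference |
|---|---|---|---|
| 20 (40 total) | 33% | 32% | about 50% |
| 40 | 58% | 53% | about 76% |
| 112 (planned) | 95% | 92% | 99% |

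Simulation error does not explain the gap. With 1,000 replicates, 87% carries ±1.96 × √(0.87 × 0.13/1000) = ±2 points, that is 85-89%.

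**Conditions that do give about 87%.**
- 40 per arm on the model-based difference at one-sided 5%: 84-86%.
- 80 independent ratings per lens on the odds ratio, 2-sided 95%: 86-87%.
- 40 crossover subjects wearing both lenses, 2-sided 95%: about 87% on the difference at an assumed latent correlation of 0.3, or 86-88% on the odds ratio at 0.6.

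None of these is two parallel arms of 20 or 40 judged on the 2-sided 95% rule.

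**Equal lenses at 112 per arm, difference rule.** Raw difference: SE = √[2p(1 − p)/112].
- Historical Control rate: SE 0.0580, power Φ(0.10/0.0580 − 1.96) = 41%.
- Historical Test rate: SE 0.0501, power Φ(0.10/0.0501 − 1.96) = 51%.
- Model-based difference, by simulation: 54-56% at the Control distribution and 78-80% at the Test distribution.

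**The case against.** **The row does not drive the trial.** SAP 7.4 says that slit lamp findings and comfort set the sample size. At 112 per arm, power with the printed historical effect is 92-99%, above the stated 87%. This stands. A reader might infer from the 50% and 76% figures that the trial is underpowered for this endpoint. The documents do not support that if the historical advantage is real.

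**The text does not assume two effects.** A reader might infer that the sizing contradicts itself, using a historical advantage in one sentence and no difference in the next. The bootstrap sentence points to the historical data, while the no-difference clause sits in the margin-conversion sentence and is most naturally confined to it. What remains is narrower: the row is not labelled as depending on the historical advantage.

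**The origin of 87% is unknown.** A reader might infer that crossover data were resampled as pairs, since the 242 ratings per lens are twice the 121 completers of one listed crossover study, or that a one-sided 5% test was used. Both are possible and neither is established. The source report is not available, the crossover account needs an assumed correlation, and no success criterion is given for this row. Nor do the neighbouring CLUE rows settle the sidedness. With the stated comfort inputs (2 points, SD 21), one-sided 5% gives Φ[7/(21 × √(2/112)) − 1.645] = 80%, not the printed 87%. For handling, the printed means and the Test SD of 18.454 give about 36%, not 63%.

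**The replacement figures depend on the model.** This also stands. Raw and model-based differences disagree by up to nearly 30 points for equal lenses. None of the figures includes site effects, covariates or the full Bayesian fit. They can serve only as guides.

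**Conclusion.** The point holds as an error in a stated power. On the SAP 10.1 rule with the historical responses, 40 subjects give about 50% power as a total and about 76% per arm on the most favourable of the three measures, against 87% printed. The shortfall is about 37 or 11 points, and larger on the odds ratio or the raw difference. The conclusion rests on two independent arms, the printed response table, a 2-sided 95% limit and likelihood-based intervals in place of the planned Bayesian model. It does not depend on how 87% arose.

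The practical consequence is about interpretation. At 112 per arm this primary is well powered if the Test advantage is real. If the lenses perform alike, approximate power is 41-56% or 51-80%, depending on the response distribution and the measure, so it is at best about the 80% target. The row as printed hides that dependence. The 0.67 margin adds a smaller mismatch, since it matches ten points only at a 50% rate.

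**What to change.** Re-run the simulation with two independent arms at 112 per arm, using the SAP 10.1 difference rule, and replace the 40-subject row in SAP Table 11 and protocol Table 12 with the result. Give the count as 224 total, the unit used in the slit lamp and comfort rows. State the assumed effect, the sidedness and the resampling unit (subject or rating, paired or independent).

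Show an equal-lenses case beside the historical-effect case, and say that power clearly above 80% relies on a real Test advantage. If the 0.67 odds ratio was the sizing criterion, say so and note that it corresponds to ten points only at a 50% rate. The values here are a rough check on the re-run, not text to insert.

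The cost is one simulation run, one table row and a few sentences in each document. Sample size and trial conduct do not change.
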